10.8 Appendix 8 - Patient-Reported Outcome Questionnaires

10.8.1 Dutch Eating Questionnaire (DEBQ)

Example of Dutch Eating Questionnaire (DEBQ)

Volunteer Name: _____ **Date:** _____

Volunteer No. _____

Please place an (✓) in the box which applies best to each of the numbered statements. All of the results will be *strictly* confidential. Most of the questions directly relate to food or eating, although other types of questions have been included. Please answer each question carefully. Thank you.

1. If you have put on weight, do you eat less than you usually do?

☐ Never ☐ Seldom ☐ Sometimes ☐ Often ☐ Very Often ☐ Not Relevant

2. Do you try to eat less at mealtimes than you would like to eat?

☐ Never ☐ Seldom ☐ Sometimes ☐ Often ☐ Very Often

3. How often do you refuse food or drink offered because you are concerned about your weight?

☐ Never ☐ Seldom ☐ Sometimes ☐ Often ☐ Very Often

4. Do you watch exactly what you eat?

☐ Never ☐ Seldom ☐ Sometimes ☐ Often ☐ Very Often

5. Do you deliberately eat foods that are slimming?

☐ Never ☐ Seldom ☐ Sometimes ☐ Often ☐ Very Often

6. When you have eaten too much, do you eat less than usual the following days?

☐ Never ☐ Seldom ☐ Sometimes ☐ Often ☐ Very Often ☐ Not Relevant

7. Do you deliberately eat less in order not to become heavier?

☐ Never ☐ Seldom ☐ Sometimes ☐ Often ☐ Very Often

8. How often do you try not to eat between meals because you are watching your weight?

☐ Never ☐ Seldom ☐ Sometimes ☐ Often ☐ Very Often

9. How often in the evening do you try not to eat because you are watching your weight?

☐ Never ☐ Seldom ☐ Sometimes ☐ Often ☐ Very Often

10. Do you take into account your weight with what you eat?

☐ Never ☐ Seldom ☐ Sometimes ☐ Often ☐ Very Often

11. Do you have the desire to eat when you are irritated?

☐ Never ☐ Seldom ☐ Sometimes ☐ Often ☐ Very Often ☐ Not Relevant

12. Do you have a desire to eat when you have nothing to do?

☐ Never ☐ Seldom ☐ Sometimes ☐ Often ☐ Very Often ☐ Not Relevant

13. Do you have a desire to eat when you are depressed or discouraged?

☐ Never ☐ Seldom ☐ Sometimes ☐ Often ☐ Very Often ☐ Not Relevant

14. Do you have a desire to eat when you are feeling lonely?

☐ Never ☐ Seldom ☐ Sometimes ☐ Often ☐ Very Often ☐ Not Relevant

15. Do you have a desire to eat when somebody lets you down?

☐ Never ☐ Seldom ☐ Sometimes ☐ Often ☐ Very Often ☐ Not Relevant

16. Do you have a desire to eat when you are cross?

☐ Never ☐ Seldom ☐ Sometimes ☐ Often ☐ Very Often ☐ Not Relevant

17. Do you have a desire to eat when you are approaching something unpleasant to happen?

☐ Never ☐ Seldom ☐ Sometimes ☐ Often ☐ Very Often

18. Do you get the desire to eat when you are anxious, worried or tense?

☐ Never ☐ Seldom ☐ Sometimes ☐ Often ☐ Very Often

19. Do you have a desire to eat when things are going against you or when things have gone wrong?

☐ Never ☐ Seldom ☐ Sometimes ☐ Often ☐ Very Often

20. Do you have a desire to eat when you are frightened?

☐ Never ☐ Seldom ☐ Sometimes ☐ Often ☐ Very Often ☐ Not Relevant

21. Do you have a desire to eat when you are disappointed?

☐ Never ☐ Seldom ☐ Sometimes ☐ Often ☐ Very Often ☐ Not Relevant

22. Do you have a desire to eat when you are bore or restless?

☐ Never ☐ Seldom ☐ Sometimes ☐ Often ☐ Very Often ☐ Not Relevant

23. Do you have a desire to eat when you are emotionally upset?

☐ Never ☐ Seldom ☐ Sometimes ☐ Often ☐ Very Often ☐ Not Relevant

24. If food tastes good to you, do you eat more than usual?

☐ Never ☐ Seldom ☐ Sometimes ☐ Often ☐ Very Often

25. If food smells and looks good do you eat more than usual?

☐ Never ☐ Seldom ☐ Sometimes ☐ Often ☐ Very Often

26. If you see or smell something delicious, do you have the desire to eat it?

☐ Never ☐ Seldom ☐ Sometimes ☐ Often ☐ Very Often

27. If you have something delicious to eat, do you eat it straight away?

☐ Never ☐ Seldom ☐ Sometimes ☐ Often ☐ Very Often

28. If you walk past the baker do you have the desire to buy something delicious?

☐ Never ☐ Seldom ☐ Sometimes ☐ Often ☐ Very Often

29. If you walk past a snack bar or a café, do you have the desire to buy something delicious?

☐ Never ☐ Seldom ☐ Sometimes ☐ Often ☐ Very Often

30. If you see others eating, do you also have the desire to eat?

☐ Never ☐ Seldom ☐ Sometimes ☐ Often ☐ Very Often

31. Can you resist eating delicious foods?

☐ Never ☐ Seldom ☐ Sometimes ☐ Often ☐ Very Often

32. Do you eat more than usual, when you see others eating?

☐ Never ☐ Seldom ☐ Sometime ☐ Often ☐ Very Often

s

33. When preparing a meal are you inclined to eat something?

☐ Never ☐ Seldom ☐ Sometimes ☐ Often ☐ Very Often

10.8.2 **Appendix 8 - Visual Analogue Scale**

Example of Visual Analogue Scale

HOW HUNGRY DO YOU FEEL RIGHT NOW?

--	--	--	--	--	--	--	--	--

NOT AT ALL EXTREMELY

HOW SICK DO YOU FEEL RIGHT NOW?

--	--	--	--	--	--	--	--	--

NOT AT ALL EXTREMELY

HOW PLEASANT WOULD IT BE TO EAT RIGHT NOW?

--	--	--	--	--	--	--	--	--

NOT AT ALL EXTREMELY

HOW MUCH DO YOU THINK YOU COULD EAT RIGHT NOW?

--	--	--	--	--	--	--	--	--

NOTHING A LARGE AMOUNT

GLP-1	Glucagon-like peptide-1
IPD	important protocol deviations
IVGTT	Intravenous glucose tolerance test
IWRS	Interactive web response system
MedDRA	Medical Dictionary for Regulatory Activities
MMTT	Mixed-meal tolerance test
PK	Pharmacokinetics
PRO	Patient reported outcome
PT	preferred term
REE	resting energy expenditure
SAE	Serious adverse event
SAP	Statistical analysis plan
SC	Subcutaneous
SOC	system organ class
SPP	Statistical programming plan
T2DM	type 2 diabetes mellitus
TEAE	Treatment-emergent adverse event

Abbreviation or Specialized Term	Definition
TEE	total energy expenditure
TESAE	Treatment-emergent serious adverse event
ULN	Upper limit of reference range
WHO-DD	World Health Organization Drug Dictionary enhanced

1 INTRODUCTION

This document describes the statistical analysis methodology for protocol D5670C00021, a Phase 2a randomised, double-blind, parallel group study to evaluate the effect of MEDI0382 on energy balance during 42 days of treatment in overweight or obese subjects with type 2 diabetes mellitus. This document details the statistical summaries relating to each study objective and describes the general conventions and definitions that will be used. In addition, a set of table templates and specifications will be included in a statistical programming plan (SPP) to complement this document.

2 STUDY OVERVIEW

2.1 Study Objectives

2.1.1 Primary Study Objective(s)

- To assess the effect of MEDI0382 titrated up to a dose level of [REDACTED] on body weight versus placebo

2.1.2 Secondary Study Objectives

- To assess the effect of MEDI0382 titrated up to a dose level of [REDACTED] versus placebo on energy intake during ad libitum lunchtime meals
- To assess the effect of a 16-day period of single-blind placebo on energy intake during an ad libitum lunchtime meal
- To assess the effect of MEDI0382 titrated up to a dose level of [REDACTED] versus placebo on TEE, AEE, and REE as measured by whole room indirect calorimetry
- To assess the effect of a 16-day period of MEDI0382 titrated up to a dose level of [REDACTED] versus placebo on REE
- To assess the effect of MEDI0382 titrated up to a dose level of [REDACTED] versus placebo on TEE as measured by doubly-labelled water
- To assess the effect of MEDI0382 titrated up to a dose level of [REDACTED] on measures of body weight and composition versus placebo
- To assess the effect of MEDI0382 titrated up to a dose level of [REDACTED] on glucose homeostasis versus placebo
- To evaluate the safety and tolerability of MEDI0382 titrated up to a dose level of [REDACTED] versus placebo
- To characterize the immunogenicity profile of MEDI0382 exposure titrated up to a dose level of [REDACTED] versus placebo

2.1.3 Exploratory Study Objectives

- [REDACTED]

[figure not shown]
- [REDACTED]
- [REDACTED]
- [REDACTED]
- [REDACTED]
- [REDACTED]
- [REDACTED]
- [REDACTED]
- [REDACTED]

2.2 Study Design

This is an exploratory Phase 2a randomised, double-blind, placebo-controlled study to evaluate the effect of MEDI0382 titrated up to [REDACTED] on energy balance in overweight or obese subjects with T2DM.

The study is planned to randomise 24 subjects at one site in the United Kingdom. Subjects will be randomised within 28 days of screening to receive single-blind placebo for 16 days, and then either double-blind MEDI0382 titrated up to [REDACTED], or placebo in a 2:1 ratio administered once daily via SC injection for 42 days (16-day single-blind and 42-day double-blind treatment periods). Subjects randomised to MEDI0382 will receive [REDACTED]

Figure 1 Study Flow Diagram

7/7 = 7 days, 28/7 = 28 days, Hood Cal = Hood-based calorimetry, DLW = doubly-labelled water, DXA = Dual X-ray absorptiometry, h = hours, IVGTT = intravenous glucose tolerance test, mins = minutes; MMTT = mixed-meal tolerance test, GET = gastric emptying time, T = time, V = visit.

2.3 Treatment Assignment and Blinding

An IWRS will be used for randomization to assign a treatment to subjects and to assign blinded investigational product kit numbers. Twenty-four (24) subjects will be randomised using a 2:1 ratio to receive either MEDI0382 (16 subjects) or placebo (8 subjects).

This is a double-blind study in which MEDI0382 and placebo prefilled syringes are identical except the fill volumes are not identical/indistinguishable in appearance. The different fill volumes of MEDI0382 and placebo prefilled syringes and the relative position of the plunger rods will be visually distinct during administration. Neither the subject/legal representative nor any of the investigator or sponsor staff who are involved in the treatment or clinical evaluation of the subjects will be aware of the treatment received. The blind will be maintained by having the study drug administered at the clinical site by an unblinded person not involved in the treatment or clinical evaluation of the subjects. This unblinded person will also dispense and receive drug from the subject and reconcile drug accountability.

2.4 Sample Size

Sixteen subjects in the MEDI0382 group and 8 subjects in the placebo group will provide > 90% power to detect a 2.5% weight change from baseline difference between [REDACTED] and placebo at Day 59, assuming a standard deviation of 2.0%, a 2-sided 0.1 alpha.

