Subjects aged ≥ 30 and ≤ 75 years, with a diagnosis of T2DM and a body mass index ≥ 28 and ≤ 40 kg/m². Female subjects of childbearing potential must not be pregnant and/or lactating, and should be using at least one highly effective method of contraception.

TREATMENT GROUPS AND REGIMENS

Following randomisation on Day -1, all eligible subjects will use placebo once daily in the morning via SC injection for 16 days during the single-blind placebo treatment period.

After the completion of the single-blind placebo treatment period, subjects will enter the double-blind treatment period, and will use either MEDI0382 or placebo in a 2:1 ratio once daily in the morning via SC injection for 42 days, as follows:

- [REDACTED]
- Placebo for 42 days (N = 8)

STATISTICAL METHODS

Sample Size: Sixteen subjects in the MEDI0382 group and 8 subjects in the placebo group will provide $> 90\%$ power to detect a 2.5% weight change from baseline difference between MEDI0382 [REDACTED] and placebo at Day 59, assuming a standard deviation of 2.0%, a 2-sided 0.1 alpha.

Statistical Analyses: The efficacy analysis will be based on the Modified Intent-to-treat (mITT) population. The primary efficacy endpoint of percentage change in body weight from Day 17 to 59 will be compared between MEDI0382 and placebo groups using an analysis of covariance (ANCOVA) model adjusting for treatment group and measurement at baseline. Last observation carried forward will be used for missing data imputation for post-baseline values when applicable. The secondary efficacy endpoints will be based on the mITT population and analysed by an ANCOVA model similar to that used for the primary efficacy analysis. Selected secondary endpoints will also be analysed using the Per-protocol population. [REDACTED]

Safety and Immunogenicity: The safety analysis will be based on the As-treated population. Adverse events (AEs) and serious adverse events (SAEs) will be coded by the most updated version of the Medical Dictionary for Regulatory Activities (MedDRA) and the type, incidence, severity, and relationship to investigational product will be summarized by MedDRA System Organ Class (SOC) and Preferred Term (PT). Specific

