3 STATISTICAL METHODS

3.1 General Considerations

Data will be presented in data listings sorted by treatment, subject number and date collected, where appropriate. Tabular summaries will be presented for each treatment. Categorical data will be summarized by treatment with the number and percentage of subjects within each category. Continuous variables will be summarized by treatment with descriptive statistics including mean, standard deviation, median, minimum, and maximum. For some variables, the geometric mean and 95% CI will be presented. Baseline values will be defined as the last valid assessment prior to the first administration of investigational product unless otherwise specified.

All available data will be included in the analyses and missing data will not be imputed, except in a last observation carried forward (LOCF) analysis and as specified in the calculation of the AUC values. When last observation carried forward (LOCF) is used to impute for missing post-baseline data, only post-baseline data will be carried forward (e.g., baseline data will not be carried forward).

All statistical tests will be 2-sided at an $\alpha = 0.10$ significance level unless stated otherwise. There will be no adjustment for multiplicity.

Data analyses will be performed using SAS[®] version 9.4 or higher (SAS Institute Inc., Cary, NC). The analytical results generated from SAS programs will follow MedImmune SAS programming standards and will be validated according to MedImmune SAS validation procedures.

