3.4.1.3 Primary Efficacy Analysis

The analysis of the primary efficacy endpoint will be performed using the mITT population. The primary efficacy endpoint of percentage change in body weight from Day 17 to 59 will be compared between MEDI0382 and placebo groups using an analysis of covariance (ANCOVA) model adjusting for treatment group and baseline weight. LOCF will be used for missing data imputation if the Day 59 evaluation is missing.

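### The stated power of more than 90% does not follow from the stated inputs, which give about 87%

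*SAP*

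**What the plan says.** SAP 2.4 gives the sample-size justification: "Sixteen subjects in the MEDI0382 group and 8 subjects in the placebo group will provide > 90% power to detect a 2.5% weight change", meaning a difference between arms in percentage weight change at Day 59. The protocol synopsis (Statistical Methods, Sample Size) makes the same claim, "assuming a standard deviation of 2.0%, a 2-sided 0.1 alpha".

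The other parts of the plan agree with these inputs. SAP 2.3 fixes 24 subjects at 2:1, so 16 and 8. SAP 3.1 says "All statistical tests will be 2-sided at an" alpha of 0.10. SAP 3.4.1.3 specifies the primary analysis as an "analysis of covariance (ANCOVA) model adjusting for treatment group and baseline weight".

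Neither readable power statement names the test or formula used, says whether the 2.0% is a raw or a covariate-adjusted SD, or gives a correlation between baseline weight and outcome. Protocol 4.8.3 (Sample Size) is redacted.

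**The concern.** The sentence supplies everything a power calculation needs: both group sizes, the difference, the SD, alpha and sidedness. It should therefore be reproducible, and it is not. It is the only readable power statement, it supports the primary endpoint, it stands in both documents, and it could well be carried into the study report. At stake is the accuracy of one planning figure. No endpoint, model, estimate or decision rule depends on it.

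**Working it through.** **Inputs**

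- Group sizes 16 and 8 (SAP 2.3 and 2.4)
- Difference 2.5 percentage points (SAP 2.4, synopsis)
- SD 2.0% (SAP 2.4, synopsis)
- Alpha 0.10, two-sided (SAP 2.4, SAP 3.1, synopsis)
- Stated power: more than 90%

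**Step 1: standard error and noncentrality**

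SE = 2.0 × √(1/16 + 1/8) = 2.0 × √0.1875 = 0.866

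Noncentrality = 2.5 / 0.866 = 2.887

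**Step 2: attempt to reproduce the stated power**

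| Method, two-sided alpha 0.10 | Critical value | Power |
|---|---|---|
| Pooled t-test, 22 df | 1.717 | 87.5% |
| ANCOVA, 21 df, 2.0% taken as residual SD | 1.721 | 87.4% |
| Normal approximation, Φ(2.887 − 1.645) | 1.645 | 89.3% |

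The t-test and ANCOVA figures come from the noncentral t distribution. A simulation of 200,000 trials gave 87.6% for the pooled t-test and 86.2% for the Welch test. None of these exceeds 90%.

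**Step 3: what would give more than 90%**

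| Changed input | Power | Status in the readable text |
|---|---|---|
| One-sided alpha 0.10, 16 vs 8, t-test | 93.9% | Contradicted: tests are two-sided |
| 12 vs 12, two-sided 0.10, t-test | 90.7% | Contradicted: allocation is 2:1 |
| ANCOVA, raw SD 2.0%, correlation 0.2 | 88.6% | No correlation stated |
| ANCOVA, raw SD 2.0%, correlation 0.3 | 90.0% | No correlation stated |
| ANCOVA, raw SD 2.0%, correlation 0.4 | 91.9% | No correlation stated |

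In the ANCOVA rows the residual SD is 2.0 × √(1 − r²). At r = 0.3 this is 2.0 × √0.91 = 1.91%. The correlations are assumptions, used to show the range.

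**Step 4: how far from 90%**

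With 16 vs 8 and the t-test, power is exactly 90% at a difference of about 2.62% (SD 2.0%), or at an SD of about 1.91% (difference 2.5%). With all stated inputs kept at 2:1, the smallest size above 90% is 18 vs 9 (90.9%).

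**Step 5: expected precision**

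90% CI half-width = 1.717 × 0.866 = 1.49, about 1.5 percentage points.

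**The case against.** The strongest reply is that the planned analysis is an ANCOVA. If 2.0% is the raw SD and baseline weight correlates with percentage weight change at somewhat above 0.3, power does exceed 90%. The redacted Protocol 4.8.3 might state such an assumption or a method. This stands as a possibility, so it cannot be said that a one-sided test and equal allocation are the sole routes to the stated figure. It does not rescue the two readable sentences, which give no correlation and do not describe the SD as unadjusted. If the sponsor relied on a covariate gain, the text needs to say so.

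A second reply is that the gap is small: 2.5 points by the t-test and 0.7 by the normal approximation, with 90% reached at planning values close to those stated. That is fair, and it settles the weight of the point. It does not make the figure right, because the documents claim strictly more than 90%.

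Three stronger readings are tempting, and the documents do not support them:

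- **A floor of 12.5% on the type II error.** That is the t-test value (100 − 87.5). The normal approximation gives 10.7%, and a covariate gain would lower it too.
- **Further loss of power through missing Day 59 weights.** SAP 3.4.1.2 and 3.4.1.3 keep such subjects in the analysis by LOCF from the double-blind period, a weight is scheduled at Day 32, and Protocol 4.1.7 allows up to five withdrawn subjects to be replaced where possible. A missing Day 59 weight does not by itself reduce the analysed number, and the documents give no attrition rate from which to compute a loss.
- **Misreading of a null result.** No readable passage ties a decision to the planned power.

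**Conclusion.** The power statement in SAP 2.4 and the synopsis is wrong as written. On the stated inputs, power is about 87% (87.5% by t-test; 87.4% by ANCOVA), and no standard two-sided calculation at alpha 0.10 on those inputs reaches 90%.

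The t-test figure assumes normal outcomes with a common SD of 2.0% and all 24 subjects analysed. The ANCOVA figure further assumes that 2.0% is already the residual SD. What the redacted Protocol 4.8.3 says is unknown.

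This is a minor correction of a stated figure. A reader might infer that the trial is materially underpowered or should be enlarged. A shortfall of about 2.5 points, in an exploratory single-site Phase 2a study tested at alpha 0.10 without multiplicity adjustment, does not support that.

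**What to change.** In SAP 2.4 and the synopsis, and in Protocol 4.8.3 if it repeats the figure, do one of the following:

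- state that 16 and 8 subjects give approximately 87% power to detect a 2.5% difference (SD 2.0%, two-sided alpha 0.10), with 90% power reached for a difference of about 2.6%; or
- keep the claim of more than 90% and state the method and the covariate assumption that produce it, including whether 2.0% is a raw or a residual SD.

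Optionally, add the expected 90% CI half-width of about 1.5 percentage points, which is useful for a trial of this size.

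The cost is one sentence in each place. Sample size, design and analysis stay as they are. Under the first option the quoted power becomes slightly less favourable.

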3 STATISTICAL METHODS

3.1 General Considerations

Data will be presented in data listings sorted by treatment, subject number and date collected, where appropriate. Tabular summaries will be presented for each treatment. Categorical data will be summarized by treatment with the number and percentage of subjects within each category. Continuous variables will be summarized by treatment with descriptive statistics including mean, standard deviation, median, minimum, and maximum. For some variables, the geometric mean and 95% CI will be presented. Baseline values will be defined as the last valid assessment prior to the first administration of investigational product unless otherwise specified.

All available data will be included in the analyses and missing data will not be imputed, except in a last observation carried forward (LOCF) analysis and as specified in the calculation of the AUC values. When last observation carried forward (LOCF) is used to impute for missing post-baseline data, only post-baseline data will be carried forward (e.g., baseline data will not be carried forward).

All statistical tests will be 2-sided at an $\alpha = 0.10$ significance level unless stated otherwise. There will be no adjustment for multiplicity.

Data analyses will be performed using SAS[®] version 9.4 or higher (SAS Institute Inc., Cary, NC). The analytical results generated from SAS programs will follow MedImmune SAS programming standards and will be validated according to MedImmune SAS validation procedures.

3.2 Analysis Populations

The analysis populations are defined in Table 1.

Table 1 Analysis Populations

Population	Description
Intent-to-treat (ITT) population	Subjects who receive any study investigational product will be included in the ITT population and subjects will be analyzed according to their randomized treatment group.
Modified Intent-to-treat (mITT) population	Subjects in the ITT population who receive at least one dose of the investigational product in the double-blind treatment period, and subjects will be analyzed according to their randomized treatment group.
As-treated population	Subjects who receive any study investigational product will be included in the as-treated population and will be analyzed according to the treatment they actually receive.
Per-protocol population	Subjects in the mITT population (receive at least one dose of the investigational product in the double-blind treatment period) who complete treatment up to Day 58.
PK population	Subjects in the As-treated population who have at least one PK sample taken with a value that is above the lower limit of quantitation.
Immunogenicity population	Subjects in the As-treated population who have at least one serum sample for immunogenicity testing.

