4.1.7 Replacement of Subjects

Subjects who withdraw from the study will be replaced where possible. A maximum number of five subjects may be replaced.

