4.8.4.3 Exploratory Efficacy and Pharmacodynamic Analyses

4.8.5 Safety

4.8.5.1 Analysis of Adverse Events

The safety analysis will be based on the As-treated population. Adverse events and SAEs will be coded by the most updated version of the Medical Dictionary for Regulatory Activities (MedDRA) and the type, incidence, severity, and relationship to investigational product by will be summarized by MedDRA System Organ Class (SOC) and Preferred Term (PT). Specific AEs will be counted once for each subject for calculating percentages. In addition, if the same AE occurs multiple times within a particular subject, the highest severity and level of relationship observed will be reported. All TEAEs will be summarized overall, by MedDRA SOC and PT, and by severity and relationship to investigational product. In addition, summaries of deaths, SAEs, and treatment discontinuations due to AEs will be provided.

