5 ASSESSMENT OF SAFETY

5.1 Definition of Adverse Events

The ICH Guideline for Good Clinical Practice E6(R1) defines an AE as:

Any untoward medical occurrence in a patient or clinical investigation subject administered a pharmaceutical product and which does not necessarily have a causal relationship with this treatment. An AE can therefore be any unfavourable and unintended sign (including an abnormal laboratory finding), symptom, or disease temporally associated with the use of a medicinal product, whether or not considered related to the medicinal product.

An AE includes but is not limited to any clinically significant worsening of a subject's pre-existing condition. An abnormal laboratory finding (including ECG finding) that requires medical intervention by the investigator, or a finding judged by the investigator as medically significant should be reported as an AE. If clinical sequelae are associated with a laboratory abnormality, the diagnosis or medical condition should be reported (eg, renal failure, haematuria) not the laboratory abnormality (eg, elevated creatinine, urine red blood cell increased). Abnormal laboratory values that are not, in the investigator's opinion, medically significant and do not require intervention should not be reported as AEs.

AEs may be treatment emergent (ie, occurring after initial receipt of investigational product) or nontreatment emergent. A nontreatment-emergent AE is any new sign or symptom, disease, or other untoward medical event that begins after written informed consent has been obtained but before the subject has received investigational product.

Elective treatment or surgery or preplanned treatment or surgery (that was scheduled prior to the subject being enrolled into the study) for a documented pre-existing condition that did not worsen from baseline is not considered an AE (serious or nonserious). An untoward medical event occurring during the prescheduled elective procedure or routinely scheduled treatment should be recorded as an AE or serious adverse event (SAE).

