3.7 Safety Analyses

The analyses of the secondary safety endpoints will be performed using the As-treated population.

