3.7.1 Adverse Events and Serious Adverse Events

Adverse events will be coded with MedDRA version 21.0 or later. Analysis of adverse events will include the type, incidence, severity and relationship to study investigational product summarized by MedDRA System Organ Class (SOC) and Preferred Term (PT), by treatment group as well as overall. The AEs summaries will include only treatment-emergent AEs, ie, those starting after the first administration of double-blind investigational product. Subjects will be counted once for specific PT or MedDRA SOC when calculating incidence rates. If the same AE Preferred Term occurs multiple times within a subject, the highest severity and level of relationship observed will be reported. Non-treatment-emergent AEs/serious adverse events (SAEs), ie, those AEs with onset after screening including during the single-blind placebo treatment but before the start of double-blind treatment will be presented in the listings. The percentage of subject with nausea, vomiting and either nausea or vomiting on each day during the dose titration period (Days 17 to 28) will be summarized with the 80% confidence interval. Note that this is not just onset of a new event but includes events where the day is included in the AE start and stop dates. A similar analysis including event rates will be performed for each of the 4-day dose titration period (Days 17-20, 21-24, and 25 to 28) and other dosing periods. Adverse events will be summarized separately for the double-blinded treatment period and for the single-blinded treatment period.

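### Subjects who stop during the placebo run-in enter the placebo denominator of the double-blind adverse event tables but can never contribute an event

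*SAP*

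**What the plan says.** **Population.** SAP 3.7 states: "The analyses of the secondary safety endpoints will be performed using the As-treated population". Protocol 4.8.5.1 agrees: "The safety analysis will be based on the As-treated population". SAP 3.2 (Table 1) admits anyone given investigational product in either period, and such subjects "will be included in the as-treated population and will be analyzed according to the treatment they actually receive". Protocol 4.8.2 has the same rule.

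**Run-in.** The regimen part of the protocol synopsis states: "Following randomisation on Day -1, all eligible subjects will use placebo once daily in the morning via SC injection for 16 days". Allocation therefore precedes a period in which both arms take the same product. Protocol 4.6.2 names placebo as investigational product.

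**Events counted.** SAP 3.7.1: "The AEs summaries will include only treatment-emergent AEs, ie, those starting after the first administration of double-blind investigational product". The same section asks for daily nausea and vomiting percentages over Days 17 to 28 with 80% confidence intervals. It sends run-in events to listings, yet ends by promising separate AE summaries for the single-blind and double-blind periods.

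**Treatment-emergent in the protocol.** Section 5.1: "AEs may be treatment emergent (ie, occurring after initial receipt of investigational product) or nontreatment emergent".

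**The concern.** The set that supplies the denominator and the rule that supplies the numerator cover different periods. Someone who takes run-in placebo and stops before Day 17 is in the As-treated set. The only treatment received is placebo, whichever arm was assigned on Day -1, and no event in that subject can start after a double-blind dose that was never given. Each such subject adds 1 to the placebo denominator and 0 to the numerator.

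With 8 planned placebo subjects, one extra person visibly changes a percentage. The nausea and vomiting percentages would include people who had stopped before the titration days being described.

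A second difficulty does not depend on dropout. An event that starts in the run-in is treatment-emergent under protocol 5.1 and not under SAP 3.7.1. Treatment-emergent AEs are part of a secondary safety endpoint, so its numerator depends on which document is followed.

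**Working it through.** The documents state no safety denominator, so there is no planned figure to reproduce. The check traces the definitions and counts.

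**Inputs**
- Planned groups: 16 MEDI0382 and 8 placebo (SAP 2.3).
- Entry to the safety set: "Subjects who receive any study investigational product will be included in the as-treated population" (SAP 3.2).
- Replacement: withdrawals are replaced where possible; "A maximum number of five subjects may be replaced" (protocol 4.1.7). This covers withdrawals at any time in the study.
- k, the number of run-in-only dropouts from either arm: not given. Range 0 to 5 assumed.
- Event counts of 4 and 2 among 8 double-blind placebo subjects: assumed for illustration.
- Subjects who take run-in placebo and then MEDI0382 are taken to count as MEDI0382. The SAP does not say so, but it is presumably intended.

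**Denominators.** If replacement restores 16 and 8 double-blind-treated subjects:
- placebo N = 8 + k
- MEDI0382 N = 16 for every k
- reported placebo percentage = x/(8+k) = (x/8) × 8/(8+k)

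| k | Placebo N | 8/(8+k) | x = 4 | x = 2 |
|---|---|---|---|---|
| 0 | 8 | 1.000 | 50.0% | 25.0% |
| 1 | 9 | 0.889 | 44.4% | 22.2% |
| 2 | 10 | 0.800 | 40.0% | 20.0% |
| 3 | 11 | 0.727 | 36.4% | 18.2% |
| 5 | 13 | 0.615 | 30.8% | 15.4% |

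If replacement is incomplete and D placebo subjects reach double-blind dosing, the multiplier is D/(D+k). For the same k this is smaller: 7/8 = 0.875 at D=7, k=1, against 8/9 = 0.889 at D=8.

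**80% intervals** (Clopper-Pearson assumed; the SAP names no method). Two events give 6.9% to 53.8% with N=8, 6.1% to 49.0% with N=9, and 4.2% to 36.0% with N=13. The interval moves down and narrows without any added information about double-blind placebo.

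**Effect on a comparison.** With an assumed 8/16 on MEDI0382 and 2/8 on placebo, the ratio is 0.500/0.250 = 2.00. With placebo N of 9, 11 and 13 it becomes 2.25, 2.75 and 3.25.

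**Which arm the dropouts come from.** With 2:1 allocation, and dropout unrelated to arm, the chance that at least one of d run-in dropouts was assigned MEDI0382 is 1 − (1/3)^d: 67% for d=1 and 89% for d=2. Placing such subjects under placebo would therefore be usual.

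**Does another rule correct this?** The mITT population requires a double-blind dose, but it groups by assigned arm and serves efficacy and patient-reported outcomes. The Per-protocol population requires treatment up to Day 58. No safety set requires a double-blind dose.

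**Treatment-emergent definitions.** Take an event starting on Day 10 in a subject who later receives MEDI0382. Protocol 5.1 makes it treatment-emergent, because placebo has been received. SAP 3.7.1 makes it non-treatment-emergent. One sentence there sends it to a listing, and the last sentence puts it in a single-blind summary.

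**The case against.** The best defence is that SAP 3.7.1 promises separate summaries by period, and a programmer could naturally use the subjects treated in each period. SAP 1 puts table templates in a programming plan that is not among the documents. SAP 3.3.1 reports subjects randomised but not given double-blind product, so a reader could see them. Counts are shown with percentages. The study is exploratory, AE summaries are descriptive, and the efficacy analyses already require a double-blind dose.

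This lowers the severity and means it is not established that the final tables will be wrong. It does not remove the point: the SAP states a population for safety, that population is too wide for these tables, and nothing in the documents gives a double-blind denominator.

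A reader might infer more than the text supports:
- **That MEDI0382 rates are diluted too.** Grouping is by treatment received, so a run-in-only subject cannot enter the MEDI0382 column.
- **That every AE is affected.** A placebo percentage of zero stays zero, and with no run-in dropouts nothing changes.
- **That five dropouts are expected.** Five limits replacements over the whole study; it neither forecasts nor caps run-in dropout.
- **That laboratory, vital-sign and ECG tables share the fault.** They are summarised by time point, and run-in dropouts have no scheduled double-blind visits, so they are largely unaffected.
- **That randomisation must move to Day 17.** Correct denominators do not need it.

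**Conclusion.** The point holds in limited form and should be fixed. On the literal text, run-in-only subjects from either arm enlarge the placebo denominator of the double-blind AE tables, including the Days 17-28 nausea and vomiting percentages, and can add no event. Non-zero placebo percentages shrink by 8/(8+k), given replacement to 8 double-blind placebo subjects. The size is unknown because k is not stated; the percentages above rest on assumed event counts.

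The bias runs one way: placebo looks better tolerated, so MEDI0382 looks worse by comparison. It would not hide harm from MEDI0382, but the tolerability contrast would still be wrong. Primary and secondary efficacy results are untouched.

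The conflict over treatment-emergent, and the two statements in SAP 3.7.1 on run-in events, stand whatever k is. Run-in events are not lost under either statement; what is unsettled is where they are counted.

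**What to change.** 1. Add a double-blind safety set to SAP 3.2 and protocol 4.8.2: subjects with one or more double-blind doses, grouped by the double-blind treatment received. Name it in SAP 3.7 and 3.7.1 and in protocol 4.8.5.1 as the denominator for the double-blind AE tables, including nausea and vomiting. With replacement to plan, the denominators are then 16 and 8 for any k. This also settles how subjects who take run-in placebo and then MEDI0382 are grouped.
2. Keep the As-treated set for the single-blind AE summary, shown as one pooled placebo column.
3. Use one treatment-emergent definition in protocol 5.1 and SAP 3.7.1. Onset after the first double-blind dose suits the between-group tables, because both arms take the same product before then.
4. In SAP 3.7.1, say whether run-in events are listed only or also summarised.

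The cost is one population definition and a few sentences across the two documents, plus the matching table specifications. Data collection, visits and the randomisation system do not change. The edits should be made before unblinding, since a denominator or event definition chosen afterwards would be post hoc.
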